13.5 Secondary Objectives, Endpoints, Analysis Plans

Secondary Endpoints (prioritized order):

In participants with precancerous gastric lesions, to determine the effect of Meriva® versus placebo on the following endpoints (comparing the change from baseline to 6 months):

- Comparison of all adverse events between Meriva® and placebo
- Comparison of changes in Histology Gastric Score (HGS) from baseline to 6 months for Meriva® versus placebo
- Additional gastric mucosal cytokine/chemokine levels (IL-8, TNF α , and IP-10 quantified by Luminex assay);
- Comparison of gastric mucosal DNA damage, as assessed by IHC, of the biomarkers 8-OHdG and H2AX;
- Associations between proinflammatory cytokine genotype status (IL-1β, IL-8, and TNFα SNPs; characterized at baseline) and the above outcomes; these will be considered exploratory analyses.

Secondary endpoint biomarker data will be assessed from gastric mucosal biopsy samples obtained during upper endoscopy. Changes in the concentrations (or categories) of these endpoints from baseline to 6 months will be explored within and between the intervention arms. Fisher's exact tests, Wilcoxon rank sum tests, and two-sample t-tests will be used to assess differences between groups. McNemar's tests, Wilcoxon signed rank tests, and paired sample t-tests will be used to assess differences within each arm. Graphical methods (i.e. boxplots, scatter plots, etc.) will also be used to describe the data. Data for these secondary biomarker endpoints will be considered hypothesis generating and/or exploratory in nature.

Proinflammatory cytokine genotype status (IL-1 β , IL-8, and TNF α SNPs) will be examined in relation to the outcomes above to further characterize the at-risk population and generate hypotheses for future studies.

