7.2.2 Screening and Baseline

Initial screening will include a review of medical/surgical history, review of baseline symptoms, assessment of vital signs, physical examination, review of concomitant medications, and baseline alcohol and tobacco use assessment. If still eligible, blood will be drawn for clinical laboratory tests (AST, ALT, Alkaline phosphatase, CBC [Platelets, Hemoglobin, WBC], BUN, Total bilirubin, Creatinine) and for research. A stool antigen test will be performed to assess *H. pylori* infection. The participant will then undergo an EGD with biopsies (surveillance and research). Three sites (antrum, corpus, and incisura) will be biopsied (See Appendix D). Histologically-confirmed MAG, GIM, or both (at a minimum of one site) are required for eligibility and will be determined by the local pathologist. Specimen images will also be collected for central analysis. However, the results of the central review are not required prior to registration/randomization. Any discrepancies between the local and central pathologists will be resolved on a case-by-case basis by the two pathologists.

Screening/baseline activities must be completed ≤ 28 days prior to Registration/Randomization.

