10.2.4 Research Tissue Specimens

Research tissue specimens will be collected at Baseline and Month 6/Post-intervention during the EGD procedures.

Biopsy specimens will be obtained during the EGD procedures. See Appendix D for locations from which the specimens will be collected. Specimens noted in Appendix D in green will be formalin-fixed and paraffin-embedded. At baseline, appropriate specimens will be sent to the local pathologist for determination of eligibility, i.e., presence of GIM and/or MAG. Remaining specimens will be used to determine Histology Gastric Score.

Specimens noted in Appendix D in red will be placed directly in screw-topped cryovials tubes with no preservative or buffer. The tubes will be snap-frozen by immersion immediately in dry ice or liquid nitrogen. To maintain the cold chain, specimens will be placed in a -70°C (or colder) freezer until shipment to BAP. See Section 10.3 for address. Shipping containers will be filled with 2-days' supply of dry ice, and all efforts necessary to prevent thaw during the shipping process will be implemented.

Biospecimen Summary

Specimen	Timepoint(s)	Processing	Shipping
Blood specimen for safety/toxicity monitoring. Specimen to be determined by local lab SOPS.	Baseline, Month 3, Month 6	Process according to local lab SOPs	Not applicable
H. pylori serology: Collect one 10mL no additive red-topped tube	Baseline	Process into serum, aliquot, freeze at -20°C or colder until shipment	Ship to BAP freezer (Address in Section 10.4) on dry ice for accessioning and storage. Storage at BAP will be at -70°C or colder; Ship in batches upon request by the University of Puerto Rico.
Mandatory: Stool testing for H. pylori antigen. Note: If a positive result is obtained, participant can be treated and then re-screened when a negative result is obtained.	Baseline	Collect and processing according to instructions in the stool antigen kit.	Not applicable
Risk genotype status: Collect one 10 mL (or two 4mL) EDTA purple- topped tube. Process using Qiagen Puregene solution in a 3:1 ratio	Baseline	Process EDTA purple topped tube into plasma and buffy coat, Freeze aliquots at -70°C or colder until shipment	Ship to BAP freezer (Address in Section 10.4) on dry ice for accessioning and storage; Storage at BAP will be at -70°C or colder; Ship in batches upon request by the University of Puerto Rico.

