13.3 Accrual and Feasibility

Planned Accrual Estimates

	DOMESTIC PLANNED ENROLLMENT REPORT Ethnic Categories					
Racial Categories	Not Hispanic or Latino		Hispanic or Latino			
	Female	Male	Female	Male	Total	
American Indian/Alaska Native	0	0	0	0	0	
Asian	0	0	0	0	0	
Native Hawaiian or Other Pacific Islander	0	0	0	0	0	
Black or African American	0	1	0	0	1	
White	1	0	5	16	22	
More Than One Race	0	0	1	1	2	
Total	1	1	6	17	25	

	INTERNATIONAL PLANNED ENROLLMENT REPORT Ethnic Categories					
1000 2000 000 100 ISS.						
Racial Categories	Not Hispanic or Latino		Hispanic or Latino		¥1. II	
	Female	Male	Female	Male	Total	
American Indian/Alaska Native	0	0	0	0	0	
Asian	0	0	0	0	0	
Native Hawaiian or Other Pacific Islander	0	0	0	0	0	
Black or African American	0	0	0	1	1	
White	1	0	5	16	22	
More Than One Race	0	0	1	1	2	
Total	1	0	6	18	25	

The study design requires a total of 100 participants for screening evaluation with approximately 50 moving forward to randomization (25 total participants per arm) due to anticipated screen failures of up to 50% prior to randomization. We further expect up to 12% of participants to drop out or otherwise become non-evaluable by 6 months, leaving 22 evaluable subjects per arm for the primary endpoint evaluation. We expect to randomize an average of 2-4 participants per month for each of the two participating CPN sites (Puerto Rico and Honduras), for an overall average accrual rate of 5-6 participants per month.

Amendment 6 Update: Because of delays related to regulatory and customs approvals, activation at Honduras was delayed by 15 months, which resulted in slower than expected overall accrual. Recently, the Honduras site discovered a higher than expected incidence of *Helicobacter pylori* infection, an exclusion criterion. In order to continue their expected recruitment pace, they expanded their outreach to more rural areas where *H. pylori* infection is somewhat less prevalent. They have also begun contacting participants who were screen failures in one previous study and who have completed another previous study as a group of known potential participants with high rates of study compliance. They are also reviewing lists of *H. pylori*-treated participants for evidence of gastric metaplasia and possible eligibility. The current anticipated completion date (last participant contact for the primary endpoint) is the 4th quarter of 2020.

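### Section 13.5 tests secondary endpoints within each arm against baseline; a Meriva effect should be read only from the baseline-adjusted comparison between arms

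*Combined protocol and SAP*

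**What the plan says.** Section 13.5 frames the secondary endpoints as the effect of Meriva against placebo. The histology endpoint is worded accordingly: "Comparison of changes in Histology Gastric Score (HGS) from baseline to 6 months for Meriva® versus placebo". Section 1.2 words its objectives the same way.

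The analysis paragraph of 13.5 then says that changes "from baseline to 6 months will be explored within and between the intervention arms". Two sets of tests follow:

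- Between arms: "Fisher's exact tests, Wilcoxon rank sum tests, and two-sample t-tests will be used to assess differences between groups". None of these adjusts for the baseline value.
- Within each arm, placebo included: McNemar's test, the Wilcoxon signed rank test, and "paired sample t-tests will be used to assess differences within each arm".

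The endpoints are listed in order of priority, but the two sets of tests are not. The plan does not say how a within-arm p-value is to be read. It does limit the strength of any claim: "Data for these secondary biomarker endpoints will be considered hypothesis generating and/or exploratory in nature".

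Entry depends on the same endoscopy that supplies the baseline tissue. Section 7.2.2 states: "Histologically-confirmed MAG, GIM, or both (at a minimum of one site) are required for eligibility".

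**The concern.** A within-arm test asks whether an arm changed over six months. The objective asks whether Meriva changed it more than placebo did. The two questions coincide only if nothing else moves the endpoint, and here other things could:

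- **Regression to the mean.** Participants enter because a baseline biopsy was positive. If the histology score carries sampling or reading error, a group selected in this way can look better at the second endoscopy without any treatment.
- **Biopsy sampling.** The second endoscopy takes new tissue, so the score can differ for that reason alone.
- **Time.** Section 13.4 itself allows for a slight fall in the placebo mean of the primary marker.

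All of these act on both arms. They cancel in the comparison between arms and remain in full in the comparison with baseline. What is at stake is the reading of a result that is significant in the Meriva arm and not in the placebo arm. That pattern is easily taken for a treatment effect although it does not test whether the arms differ. These results are meant to generate hypotheses, so a false lead could carry into later work.

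**Working it through.** **The plan's own figure.** Sections 13.3 and 13.4 give 22 evaluable participants per arm. Section 13.4 assumes mean decreases of 7 and 0.5 pg/mg (difference 6.5), SD 7.5, one-sided 0.05, and states 88% power. The noncentrality is 6.5 / (7.5 × √(2/22)) = 2.87 on 42 degrees of freedom, which gives 88.2% (normal approximation 89.1%). The stated power is reproduced. The documents give no power, SD, reliability or expected drift for the secondary endpoints.

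**Within-arm test when Meriva does nothing.** Assume that both arms share the same mean change of d standard deviations of the change, with 22 participants per arm and a paired t-test at two-sided 0.05. The values of d and the two-sided level are assumptions. The noncentrality is d × √22 = 4.69d on 21 degrees of freedom. Let p be the probability of significance in one arm. The arms are independent, so the probability of significance in Meriva but not placebo is p(1 − p).

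| Shared change d | Noncentrality | Meriva arm significant (p) | Meriva but not placebo, p(1 − p) | Between-arm test |
|---|---|---|---|---|
| 0 | 0 | 5.0% | 4.8% | 5% |
| 0.1 | 0.47 | 7.3% | 6.8% | 5% |
| 0.2 | 0.94 | 14.6% | 12.5% | 5% |
| 0.3 | 1.41 | 26.9% | 19.7% | 5% |
| 0.4 | 1.88 | 43.3% | 24.5% | 5% |
| 0.5 | 2.35 | 60.9% | 23.8% | 5% |

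The last column is constant because a shared shift cancels in the difference between arms.

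**Is that range of d plausible for the histology score?** A simulation selected participants on a noisy baseline score, with no treatment effect. Observed scores have variance 1 and reliability r, and the top fraction of baseline scores enters. The expected change is −(1 − r) × the mean baseline among those selected. For the top 50% that mean is 0.80, so r = 0.5 gives −0.40. The simulated SD of change is 0.917, so d = 0.40 / 0.917 = 0.44.

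| Fraction entering | r = 0.9 | r = 0.8 | r = 0.7 | r = 0.5 |
|---|---|---|---|---|
| Top 50%: Meriva arm significant | 13% | 22% | 30% | 50% |
| Top 80%: Meriva arm significant | 7% | 8% | 10% | 13% |
| No selection | 5% | 5% | 5% | 5% |

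The between-arm test stayed between 4.6% and 5.2% throughout. The 50% row is an upper bound. Section 13.3 plans for 100 screened "due to anticipated screen failures of up to 50% prior to randomization", but those failures also include *H. pylori* infection and other reasons.

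**What adjustment for baseline adds.** Assume equal variance σ² at both visits and correlation ρ between them. A change score has variance 2σ²(1 − ρ), and a baseline-adjusted outcome has σ²(1 − ρ²). The ratio of adjusted to unadjusted is (1 + ρ)/2, which is 0.75 at ρ = 0.5 and 0.95 at ρ = 0.9. Both values of ρ are illustrative. Adjustment also removes the effect of a chance baseline imbalance, which regression to the mean would otherwise turn into a difference in change.

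**The case against.** The strongest reply is that the randomized comparison is already planned. The objectives are worded as Meriva against placebo, between-arm tests are named first, placebo receives the same within-arm tests, and the biomarker results are labelled exploratory. All of this stands. A reader might infer that shared changes *will* be reported as treatment findings, or that the placebo arm is wasted. The documents support neither: nothing in them says that significance in one arm only will be taken as evidence. What remains is that nothing excludes it either. Section 13.8 bars sub-analyses from supporting efficacy conclusions, but no such limit is placed on the within-arm tests. The exploratory label weakens a claim without changing what the test compares.

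The selection mechanism also has limits. Entry is the presence of a lesion, not a threshold on the histology score. Section 3 says that candidates are pre-selected with a confirmed or suspected diagnosis, so for some the baseline endoscopy only confirms a known lesion. IL-8, TNFα, IP-10, 8-OHdG and H2AX are not entry criteria, so selection reaches them only through their correlation with the lesion. This stands, and it confines the regression argument mainly to the histology score.

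The shift sizes are assumptions, and at 0.1 SD the excess is small (7.3% against 5%). This also stands.

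A further inference is tempting from Section 10.2.4, which says, after describing the eligibility reading, "Remaining specimens will be used to determine Histology Gastric Score". A reader might conclude that the baseline score uses different tissue from the Month 6 score. The documents do not establish this. The specimen table in that section and Section 10.3 provide for scoring tissue from both endoscopies, and the biopsy map in Appendix D is not visible in the available text. No part of this point rests on it.

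**Conclusion.** The point holds as a gap in the analysis plan. Section 13.5 gives within-arm significance tests the same standing as between-arm tests for a between-arm objective, and a within-arm test cannot isolate Meriva. With no treatment effect and an assumed shared change of 0.1 to 0.5 SD, the Meriva arm is significant in 7% to 61% of trials, and Meriva but not placebo in 7% to 25%, against about 5% for the between-arm test. These rates assume 22 evaluable participants per arm, a two-sided 0.05 level and normally distributed changes. The documents give no figure for the shared change, so they show how the error behaves and do not predict it for this trial.

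The scope is limited. The primary endpoint, the sample size and the validity of the planned between-arm tests are untouched. Misleading secondary findings are possible, chiefly for the histology score, but not inevitable.

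**What to change.** In Section 13.5:

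1. Replace the McNemar, signed rank and paired t-tests with descriptive within-arm changes (estimate and confidence interval), without p-values.
2. State that any statement about a Meriva effect on a secondary endpoint rests only on the between-arm contrast.
3. Make that contrast baseline-adjusted: ANCOVA of the Month 6 value on arm and baseline value for the continuous markers, and a rank-based or ordinal equivalent for skewed markers and the histology score.

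The cost is a change of wording. The baseline values are already collected, no visits, specimens or participants are added, and fewer tests are run. The adjustment uses one degree of freedom for the baseline term and generally gains precision. The exploratory label can stay as it is.

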13.6 Reporting and Exclusions

All randomized participants who are evaluated at baseline and 6 months and have IL-1 β cytokine levels from those time points will be evaluable for the primary endpoint of this study using the modified intent-to-treat principle. We plan to over-randomize assuming 12% drop out within 6 months to ensure an adequate sample size in the primary analysis cohort. There will be

no imputation for missing data. A summary and listing of all major protocol violations will be provided. All details will be given in the final study report and/or manuscript. Participants lost to follow-up will be censored on the last date of assessment (or contact) and as appropriate for analyses that are dependent upon length of study participation.

13.7 Evaluation of Toxicity (secondary endpoint)

All participants will be evaluable for adverse events (AEs) from the time of their first dose of Meriva® or placebo. To evaluate the AE profiles associated with each arm, the maximum grade for each type of adverse event will be recorded for each participant and frequency tables will be reviewed to determine the overall patterns. The number and severity of adverse events (overall and by intervention group) will be tabulated and summarized. Grade 3+ adverse events will be similarly described and summarized separately. As per NCI CTCAE, toxicities are defined as adverse events that are classified as either possibly, probably, or definitely related to the interventional agent. Overall toxicity incidence, as well as toxicity profiles will be explored and summarized within and between the 2 intervention arms. Frequency distributions, graphical techniques, and other descriptive measures will form the basis of these analyses. In addition, we will review all adverse event data that are graded as 3, 4, or 5 and classified as either "unrelated or unlikely to be related" to the study intervention in the event of an actual association developing.

13.7.1 Adverse Event Stopping Rule

The trial will be monitored closely for occurrence of adverse events by the study team and by the Mayo Clinic Cancer Center Data Safety and Monitoring Board (DSMB) using the adverse event (AE) stopping rule specified below:

Adverse Event Stopping Rule: The stopping rule specified below is based on the knowledge available at study development. We note that the Adverse Event Stopping Rule may be adjusted in the event of either (1) the study re-opening to accrual after any temporary suspension or (2) at any time during the conduct of the trial and in consideration of newly acquired information regarding the adverse event profile of the treatment(s) under investigation. The study team in consultation with the Mayo DSMB may also choose to suspend accrual because of unexpected adverse event profiles that have not crossed the specified rule below.

Across all participants, accrual will be temporarily suspended to this study if at any time we observe events considered at least possibly related to study treatment (i.e., an adverse event with attribute specified as "possible", "probable", or "definite") that satisfy any of the following criteria for each arm separately:

If at any time 2 of the initial 10 treated participants or 20% of all participants (i.e. when accrual is greater than 10 participants) have experienced a grade 3 or higher adverse event.)

If at any time 1 participant experiences a Grade 4 or 5 AE that is at least possibly related to concomitant use of CYP sensitive substrate medications.

Each grade 5 event will be reviewed on a case by case basis in a real time fashion to determine whether study accrual should be suspended. We will also review all grade 4 adverse events regardless of attribution to monitor the emergence of any previously unrecognized treatment related adverse event.

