5.1 Dose Regimen and Dose Groups

- Meriva®/matching placebo capsules
- 1000 mg (two 500 mg capsules)/day
- Duration 180 days (+/- 14 days)

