12.4 Data and Safety Monitoring Plan

The CPN Master DSMP, applicable to all studies within the CPN Consortium, has been modified for the purposes of this study. The MAY2015-05-01 DSMP provides detailed information regarding data and safety monitoring for this study. The trial will be monitored closely for occurrence of adverse events by the study team and by the Mayo Clinic Cancer Center Data Safety Monitoring Board (DSMB). The DSMB (along with the study Medical Monitor) will be consulted regarding whether or not accrual should be suspended to allow for investigation in the occurrence of severe adverse events, particularly for those that are possibly, probably, or definitely related to the study agent.

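### Crossing the adverse event stopping rule triggers a stated decision about accrual only, not about other participants still on blinded agent, and after the last randomization that one action cannot be taken

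*Combined protocol and SAP*

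**What the plan says.** Section 13.7.1 states the consequence of the rule in one sentence: "Across all participants, accrual will be temporarily suspended to this study if at any time we observe events considered at least possibly related" to the study agent and satisfying either of two criteria, applied arm by arm. The first criterion counts grade 3 or higher events: "If at any time 2 of the initial 10 treated participants or 20% of all participants (i.e. when accrual is greater than 10 participants" have had one. The second concerns medications that are sensitive CYP substrates: "If at any time 1 participant experiences a Grade 4 or 5 AE that is at least possibly related to concomitant use" of such drugs.

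The rest of the section points the same way. Below the threshold, the study team and DSMB "may also choose to suspend accrual because of unexpected adverse event profiles that have not crossed the specified rule below". Each grade 5 event is reviewed "in a real time fashion to determine whether study accrual should be suspended". All grade 4 events are also reviewed, with no action stated.

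Section 12.4 provides for close adverse event monitoring by the study team and DSMB. The specific question it gives the DSMB and medical monitor is again enrolment: they "will be consulted regarding whether or not accrual should be suspended to allow for investigation in the occurrence of severe adverse events". It also refers to a study-specific data and safety monitoring plan (DSMP) for detail.

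On timing, Section 5.1 gives "Duration 180 days (+/- 14 days" in either direction, and Section 13.3 plans "for an overall average accrual rate of 5-6 participants per month". Its Amendment 6 update reports slower accrual than expected and gives no achieved rate.

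**The concern.** The rule counts events among people already treated, over the whole period of treatment, but its stated action reaches only people not yet enrolled.

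This leaves two gaps. If the boundary is crossed during accrual, nothing says that anyone must decide what happens to the other participants then taking capsules. If it is crossed after the last randomization, there is no accrual left to suspend, so the rule has no stated effect at all.

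Safety and tolerability is the first-listed secondary objective. Toxicity that emerges late in a six-month course, or a proportion that first reaches 20% when the arms are nearly full, is what such a rule should bring to a decision.

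**Working it through.** **What each provision does.** The plan gives no figure for this point, so the first check is to set the provisions side by side.

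- 13.7.1, both triggers: suspend accrual.
- 13.7.1, discretion below the threshold: suspend accrual.
- 13.7.1, grade 5 review: decide whether to suspend accrual.
- 13.7.1, grade 4 review: no action stated.
- 12.4, DSMB consultation: whether to suspend accrual so that events can be investigated.
- 5.6 and 8.3: interruption or stopping of agent for an individual participant.
- 8.5: the sponsor's general right to end the study.

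The last two act on people who are dosing, but neither is tied to a boundary crossing.

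**How much dosing follows the last randomization.** Inputs: 50 participants randomized (13.4), 6 months of dosing each (5.1), accrual rate r per month (13.3). Assumptions: even accrual, dosing from randomization, full-length dosing, no dropout.

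- Accrual time = 50/r.
- Participants on agent at the last randomization = 6r.
- Person-months still to come = sum of (6 − k/r) for k = 0 to 6r − 1, which is 18r + 3.
- Total planned = 50 × 6 = 300 person-months.

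| r per month | accrual (months) | on agent at last randomization | person-months after it | share of 300 |
|---|---|---|---|---|
| 2 (assumed) | 25 | 12 | 39 | 13% |
| 5 | 10 | 30 | 93 | 31% |
| 5.5 | 9.1 | 33 | 102 | 34% |
| 6 | 8.3 | 36 | 111 | 37% |

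Treating accrual as continuous gives 18r instead: 90 to 108 person-months at 5 to 6 per month (30% to 36%), and 36 (12%) at 2 per month. If accrual took 36 months (also an assumption), r = 50/36 = 1.4, about 8 participants would be on agent at the last randomization, and 18 × 50/36 = 25 person-months (8%) would follow it.

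Section 6.8.2 allows up to 14 days from registration to first dose. With the 14-day window in 5.1, the longest tail after the last randomization is 14 + 180 + 14 = 208 days.

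**Whether a late crossing is possible.** The first criterion is cumulative. In a full arm of 25 it is met at 0.20 × 25 = 5 participants. After accrual closes the denominator is fixed, so the proportion can only stay the same or rise. The second criterion needs one participant and can be met at any point while dosing continues.

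**The case against.** A reader might infer that participants on agent are unprotected, or that the rule does nothing for them. The documents do not support that. Section 5.6 provides for interruption of agent in anyone with an event at least possibly related to it, which covers every participant whose event counts towards the rule. For users of CYP substrates that provision starts at grade 2. Off-agent criteria (8.3), weekly calls (7.3), contact with the medical monitor within 24 hours of learning of a serious event (11.2.2), grade 4 and 5 review, general DSMB monitoring and the sponsor's right to stop (8.5) all continue after accrual closes. Suspension is meant to allow investigation, so a crossing during accrual does bring events before people who can act. All of this stands, and it narrows the gap to the other participants, those without an event of their own.

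A second tempting reading is that everyone must keep dosing after a crossing. No section says so; the plan is silent. A third is that the sections contradict each other. They do not: 13.7.1 and 12.4 agree, and the difficulty is that their shared action is narrower than what the rule counts.

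It is also fair to say that a crossing may be unlikely. Section 6.2 puts each listed side effect at 3 or fewer per 100. If related grade 3 or higher events had an illustrative 3% rate, the chance of at least 5 in an arm of 25 is about 0.0008. At 10% it is about 0.10 and at 20% about 0.58 (one look at a full arm). A safety rule exists for the case where the expected rate proves wrong, so this limits the urgency but does not close the gap. The second trigger needs only one event.

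Finally, the DSMP may already state the missing decision. That cannot be checked here.

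**Conclusion.** The point holds as a limit on the stated action. Crossing a boundary leads, on the text available, to a decision about accrual and to no stated decision about other participants on blinded agent. After the last randomization even that action is unavailable. The continuing safeguards are real, but none is triggered by a crossing.

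The number of participants affected is uncertain because the achieved accrual rate is not given. A reader might take 30-36 participants and 31-37% of exposure as the expected size. Those figures hold only at the planned 5-6 per month, and Section 13.3 reports that accrual was slower. At an assumed 2 per month the figures are 12 participants and 13%. All counts combine Meriva and placebo; with 1:1 allocation about half would be on Meriva. They rest on even accrual, full six-month dosing and no dropout.

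Slower accrual shrinks the second gap but leaves the first, which applies to any crossing while others are dosing. The second was also still ahead at Amendment 6 (May 2019), which expected the last primary-endpoint contact in the fourth quarter of 2020. This is a worthwhile, inexpensive improvement. Confidence is medium because the DSMP was not seen.

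**What to change.** Amend 13.7.1 and 12.4 to state two things:

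1. The rule applies until the last participant's last dose.
2. A crossing, during or after accrual, requires the DSMB and medical monitor to make and record a decision about participants currently on agent as well as about accrual.

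If the DSMP already says this, a cross-reference from both sections is enough; otherwise it should carry the same text. What the decision should be is for the sponsor and DSMB, and this point proposes no clinical action.

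The cost is about two sentences in an amendment. The downside is that the DSMB may have to convene after accrual has closed.
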